10.1.3 Local laboratory values

Box plots of local laboratory values will be generated for baseline values and for values measured during the course of the study by treatment arm and visit. Each box plot will show the first quartile, the median, and the third quartile. Outliers (values outside the box plot) will also be plotted. If appropriate, horizontal lines representing boundaries for abnormal values will be plotted.

For each local laboratory measure, summary statistics will be presented by treatment arm and timepoint, as well as for changes between baseline and post-enrollment. In addition, the number (percentage) of participants with local laboratory values recorded as meeting Grade 1 AE criteria or above as specified in the Division of AIDS Table for Grading the Severity of Adult and Pediatric Adverse Events will be tabulated by treatment arm for each postvaccination timepoint. Reportable clinical laboratory abnormalities without an

associated clinical diagnosis will also be included in the tabulation of AEs described above.

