5.1.1 Inclusion criteria

1. Able and willing to complete the informed consent process, including an Assessment of Understanding: volunteer demonstrates understanding of this study; completes a questionnaire prior to first vaccination with verbal demonstration of understanding of all questionnaire items answered incorrectly.
2. 18-55 years old, inclusive, on day of enrollment.
3. Agrees to comply with planned study procedures and be available for clinic follow-up through the last clinic visit.
4. Agrees not to enroll in another study of an investigational agent during participation in the trial. If a potential participant is already enrolled in another clinical trial, approvals from the other trial sponsor and the HVTN 302 PSRT are required prior to enrollment into HVTN 302.
5. In good general health according to the clinical judgement of the site investigator.
6. Physical examination and laboratory results without clinically significant findings that would interfere with assessment of safety or reactogenicity in the clinical judgement of the site investigator.

7. Assessed as low risk for HIV acquisition per low risk guidelines (see [Appendix H](#)), agrees to discuss HIV infection risks, agrees to risk reduction counseling, and agrees to avoid behavior associated with high risk of HIV exposure through the final study visit. Low risk may include persons stably taking pre-exposure prophylaxis (PrEP) as prescribed for 6 months or longer.
8. Hemoglobin
 - ≥ 11.0 g/dL for volunteers who were assigned female sex at birth
 - ≥ 13.0 g/dL for volunteers who were assigned male sex at birth and transgender males who have been on hormone therapy for more than 6 consecutive months
 - ≥ 12.0 g/dL for transgender females who have been on hormone therapy for more than 6 consecutive months
 - For transgender participants who have been on hormone therapy for less than 6 consecutive months, determine hemoglobin eligibility based on the sex assigned at birth
9. White blood cell (WBC) count $> 3,500/\text{mm}^3$
10. Platelets $\geq 125,000 / \text{mm}^3$
11. Alanine aminotransferase (ALT) $< 2.5 \times$ upper limit of normal (ULN) based on the institutional normal range
12. Serum creatinine $\leq 1.1 \times$ ULN based on the institutional normal range
13. Negative results for HIV infection by an (US) Food and Drug Administration (FDA)-approved enzyme immunoassay (EIA) or chemiluminescent microparticle immunoassay (CMIA).

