9.4 Safety monitoring

9.4.1 Protocol Safety Review Team (PSRT)

The PSRT comprises the Study Chairs, participating CRS PI(s), HVTN Protocol Team Leader, DAIDS Medical Officer, HVTN Clinical Safety Specialist (CSS), and other Study Clinicians. The Protocol Team clinic coordinator, clinical data manager, vaccine developer representative, clinical trial manager, and others may also be included in HVTN 302 PSRT meetings. The PSRT will review study safety information on a weekly basis through two weeks after the last participant receives the final study injection. Because participants can be enrolled in the study with a Grade 1 ALT value (up to $<2.5 \times \text{ULN}$), the PSRT will monitor all gradable ALT abnormalities reported as adverse events. Less frequent safety reviews will be conducted at the discretion of the PSRT.

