11 SAFETY TABLES, PARTICIPANT LISTINGS, AND FIGURES

11.1 List of Tables

The following tables are included in the SMB reports and FSR for Safety:

- Enrollment Report
- Demographics and Vaccination Frequencies
- Overall Protocol Status
- Maximum Local and Systemic Reactogenicity Summaries
- Adverse Experiences by Body System and Severity – By Decreasing Frequency
- Adverse Experiences by Preferred Term and Severity – By Decreasing Frequency – Includes Severe, Life-threatening or Fatal Experiences Only
- Adverse Experiences by Preferred Term and Severity – By Decreasing Frequency – Includes Experiences of All Severities
- Adverse Experiences by Preferred Term and Relationship to Study Product – By Decreasing Frequency – Includes Related Experiences Only
- Adverse Experiences by Preferred Term and Relationship to Study Product – By Decreasing Frequency – Includes Experiences of Any Relationship
- Expedited Adverse Experiences (EAEs) Reported to the Regulatory Support Center (RSC)
- Pregnancy Listing

Additional tables included in the FSR for Safety:

- Social Impact Summary
- FNA/Leukapheresis Related Events
- Listing of Urticaria Adverse Events
- End of Study Diagnostic Testing Results for Vaccinees
- Local Lab Value Summary Statistics
- Local Laboratory Values Meeting Grade 1 AE Criteria or Above

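### The table of Grade 1 or above laboratory values ignores the grade at entry, although Grade 1 ALT is allowed at enrolment

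*SAP*

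**What the plan says.** SAP 10.1.3 counts participants with "local laboratory values recorded as meeting Grade 1 AE criteria or above", and says that the count "will be tabulated by treatment arm for each postvaccination timepoint". Protocol 6.3.3.3 has the same rule. Neither text asks whether the grade was already present at entry or has risen since.

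Baseline appears twice elsewhere in SAP 10.1.3. "Box plots of local laboratory values will be generated for baseline values", and summary statistics are planned by arm and timepoint, "as well as for changes between baseline and post-enrollment". The section does not say which value is the baseline.

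SAP 11.1 lists "Local Laboratory Values Meeting Grade 1 AE Criteria or Above" and a table of laboratory summary statistics among the additional tables of the Final Study Report (FSR). It lists no shift table and no table of new or worsened grades. The listings and figures in SAP 11.2 and 11.3 do not supply one.

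On entry, inclusion criterion 11 (Protocol 5.1.1) admits ALT below 2.5 times the "upper limit of normal (ULN) based on the institutional normal range". Protocol 9.4.1 draws the consequence: "Because participants can be enrolled in the study with a Grade 1 ALT value", the Protocol Safety Review Team (PSRT) will "monitor all gradable ALT abnormalities reported as adverse events". That is a monitoring step. No analysis rule goes with it.

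**The concern.** Laboratory measures are part of primary endpoint 1. The trial has no placebo arm (Protocol 2.3), so nothing shows how often Grade 1 values would occur without vaccine. A participant's own entry value is the natural control, and the graded count does not use it.

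A participant who enters with Grade 1 ALT and stays there is counted in the same cell as one whose ALT rose after vaccination. With 18 per arm, one or two such participants change the percentage visibly (1/18 = 5.6%, 2/18 = 11.1%). A reader of the FSR could not tell how many of those counted had worsened.

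**Working it through.** **1. How often an entry elevation can be counted.** The ALT row in Protocol Appendices A and B has four 5 mL entries, but the tables are broken in extraction, so I placed the draws from the visit totals (mL, Appendix B).

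- Screening: 5 (hepatitis) + 5 (HIV) + 5 (CBC) + 5 (ALT/creatinine) = 20.
- Visits 03, 07 and 11: 5 (CBC) + 5 (ALT/creatinine) + 5 (storage) = 15 each.
- Visits 02 and 04: 42.5 + 25.5 = 68 each. No room for ALT.
- Visit 06: 85 + 25.5 = 110.5. No room.
- Visit 08: 144.5 + 25.5 + 10 = 180. No room.
- Visit 10: 85 + 25.5 + 10 = 120.5. No room.
- Visit 12: 204 + 25.5 = 229.5. No room.
- Visit 14: 25.5 + 10 + 5 = 40.5. The CBC row has five entries and the ALT row four, so this 5 mL is the fifth CBC.
- Visit 15: 255 + 25.5 + 20 = 300.5. No room.

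Visits 05, 09 and 13 (Appendix A only) total 25.5, which is the serum draw alone. ALT is therefore apparently measured at screening and about one week after each vaccination. A persistent entry elevation could be counted at up to three timepoints. The baseline is the screening value, which may be up to 56 days before Day 1.

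**2. Check of the method.** The documents state no figure for Grade 1 laboratory abnormalities, so there is none to reproduce. The formula used below, P(at least one) = 1 − (1 − p)^18, can be checked against Protocol Table 6-4. For p = 10%, 20% and 30% it gives 0.850, 0.982 and 0.998, against the stated 0.85, 0.98 and 1.

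**3. Size with no vaccine effect.** The arm size of 18 is from the schema. The share entering with Grade 1 ALT (e) and the share of those still Grade 1 at a given draw (s) are not in the documents. I assume e = 2%, 5% or 10% and s = 50% or 100%. With q = e × s, the expected count per arm is 18q. The last column is the binomial probability that two given arms differ by at least two participants.

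| e | s | q | 18q | P(at least one in an arm) | P(two arms differ by 2 or more) |
|---|---|---|---|---|---|
| 2% | 50% | 0.010 | 0.18 | 0.165 | 0.023 |
| 2% | 100% | 0.020 | 0.36 | 0.305 | 0.072 |
| 5% | 50% | 0.025 | 0.45 | 0.366 | 0.099 |
| 5% | 100% | 0.050 | 0.90 | 0.603 | 0.227 |
| 10% | 50% | 0.050 | 0.90 | 0.603 | 0.227 |
| 10% | 100% | 0.100 | 1.80 | 0.850 | 0.391 |

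**4. Effect on a real signal.** Suppose that 5% of participants not already at Grade 1 develop it (assumption) and that entry elevations persist fully. The tabulated rate is q + (1 − q) × 0.05:

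- e = 2%: 0.02 + 0.98 × 0.05 = 6.9%
- e = 5%: 0.05 + 0.95 × 0.05 = 9.75%
- e = 10%: 0.10 + 0.90 × 0.05 = 14.5%

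The table alone cannot separate the two parts of these rates. A count of grades above baseline would give zero for every unchanged entry elevation.

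**The case against.** The strongest reply is that baseline is not ignored. Change summaries rest on each participant's own change. The box plots show baseline by arm, with outliers plotted and, where appropriate, lines at the abnormal boundaries. Entry elevations could well be visible there with 18 per arm. SAP section 6 also has adverse-event analyses take account of relationship to product, and the PSRT watches gradable ALT. All of this stands, and it lowers the risk of a serious misreading. It does not close the gap, because none of these outputs links a participant's post-vaccination grade to that participant's entry grade.

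Little depends formally on this table. It has no test or success criterion, and SAP 11.1 places it in the FSR and not in the Safety Monitoring Board reports. That also stands, and it limits the point to reporting.

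A reader might infer more than the documents support:

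- *Entry abnormalities recur at every visit.* The blood volumes point to three post-vaccination ALT draws at most.
- *The problem affects laboratory values generally.* Grade 1 at entry is documented only for ALT. Whether other entry limits overlap Grade 1 depends on the DAIDS grading table, which the documents do not reproduce.
- *Comparisons between arms are biased.* Arms are randomised within each part, so entry elevations there produce chance imbalance and not systematic bias.
- *The wide interval for 2/18 in Protocol Table 6-5 measures the problem.* That width reflects the arm size alone and would be the same for two new-onset cases.

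**Conclusion.** The point holds as a gap in reporting. Followed as written, SAP 10.1.3 counts an unchanged entry ALT elevation as a post-vaccination abnormality at each ALT draw. Descriptive counts are inflated and can differ by chance between arms of 18, with no placebo arm to show the background.

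The expected excess is about 0.2 to 1.8 participants per arm at each draw. This rests on assumed entry rates of 2% to 10% and persistence of 50% to 100%. It is an average: even at 10% with full persistence, 15% of arms would show no such participant (1 − 0.850). If few or no participants entered with Grade 1 ALT, the effect is negligible, and baseline data already held by the sponsor would show this.

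A reader might conclude that the laboratory part of primary endpoint 1 is unsound. The documents do not support that, since the other planned displays remain usable and no inference is drawn from this table.

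**What to change.** Keep the Grade 1 or above table, which Protocol 6.3.3.3 specifies. Add to SAP 10.1.3 and to the FSR tables in SAP 11.1, by arm:

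- a shift table of baseline grade against worst post-vaccination grade;
- a count of participants whose post-vaccination grade is higher than at baseline.

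Define baseline as the last value before first vaccination. For ALT that is apparently the screening draw.

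The cost is a few lines of SAP text and a small amount of programming on data already collected, with no new visits or samples. The limitation is that baseline is a single value that may be up to 56 days old. Ordinary fluctuation around the grading boundary may therefore appear as worsening or hide it. A table footnote should say so, and the all-grades table beside it lets the reader see both counts.

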10.1.4 Reason for vaccination discontinuation and early study termination

The number and percentage of participants who discontinue vaccination and who terminate the study early will be tabulated by reason and treatment arm.

10.2 Analyses to investigate related urticaria adverse events

The following analyses will be conducted to generate potential explanations of the related urticaria adverse events observed in HVTN 302.

Urticaria cases are defined as participants who report any adverse event of urticaria (medDRA preferred term) of any duration deemed related to study product. Urticaria non-cases are defined as participants who do not report any such event.

Differences in baseline variables identified by the HVTN 302 protocol team leadership will be formally compared between urticaria cases and non-cases by Barnard's exact test for the following 15 binary variables at enrollment: female sex at birth, Hispanic or Latino ethnicity, race = White given data sparsity, history of eczema, history of seasonal and environmental allergies, history of food allergies, history of drug allergies, history of other and non-specified allergies, and use of antihistamine/asthma inhaler/steroid medications, COVID-19 infection, mRNA COVID-19 vaccination (Moderna or Pfizer), any Moderna COVID-19 vaccination, any Pfizer COVID-19 vaccination, Moderna received as last COVID-19 vaccination, Pfizer received as last COVID-19 vaccination. The Wilcoxon rank sum test will be used to evaluate differences in distribution of age in years at enrollment between urticaria cases and non-cases. Multiplicity adjustment of the p-values for comparing each of these 16 demographic characteristics and prior histories between participants with and without urticaria will be done to control the family-wise error rate at 0.05 using Holm, 1979 adjustment. For covariates where the unadjusted p-value was less than 0.05 for the association with urticaria, odds ratios (OR) and nominal 95% CIs were calculated by median-unbiased estimation (mid-p) method [1] with Haldane-Anscombe correction for 0 counts [2].

Tables

- Demographics (sex at birth, ethnicity, race, age in years), prior conditions and use of allergy medications (history of eczema, history of seasonal and environmental allergies, history of food allergies, history of drug allergies, history of other and non-specified allergies, use of antihistamine/asthma inhaler/steroid medications at enrollment), Covid-19 infection prior to enrollment, receipt of any Covid-19 mRNA vaccination prior to enrollment, receipt of any Moderna Covid-19 mRNA vaccination prior to enrollment, receipt of Moderna as last Covid-19 mRNA vaccination prior to enrollment. Stratified by urticaria case/non-case status, summarized by n/N, % for binary/categorical variables and by 25%, median, 75% for age in years.
- Covid-19 vaccination post-enrollment stratified by urticaria case/non-case status, summarized by n/N (%).

Figures

- Timeline of vaccination times (grey open circles), blood draws (red points), and urticaria AE onset and resolution (salmon line segments or arrows if no resolution) for urticaria cases where x-axis denotes study weeks from enrollment and y-axis denotes ptid (study group).
- Boxplots of days from last mRNA Covid-19 vaccination to enrollment for urticaria cases and non-cases, with different point types denoting Pfizer (triangle) vs. Moderna (filled circle) vaccine.
- Boxplots of days from last Moderna Covid-19 vaccination to enrollment for urticaria cases and non-cases.
- Spaghetti plots of eosinophil and basophil counts over time with red lines denoting urticaria cases and grey dashed lines indicating non-cases.

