9.6 Sentinel Safety Reviews

Enrollment will start with Groups 1-3 simultaneously until a total of 12 participants, approximately 4 participants in each group (Part A sentinel safety cohort) have been enrolled. Enrollment will then pause. The PSRT will review cumulative safety information recorded through the safety visit scheduled two weeks post first vaccination and will determine whether it is safe to proceed with enrolling the participants in Groups 4-6 and the rest of Groups 1-3.

Enrollment will then start again for the first 12 participants in Groups 4-6 (Part B sentinel safety cohort) and the rest of Part A (Groups 1-3) in parallel. Once the Part B sentinel safety cohort (Groups 4-6) has been fully enrolled, enrollment in Groups 4-6 will then pause while the remainder of Part A (Groups 1-3) continues enrollment. The PSRT will review cumulative safety information recorded for Groups 4-6 (Part B sentinel safety cohort) through the safety visit scheduled two weeks post first vaccination and will determine whether it is safe to proceed with enrolling the remainder of participants in Groups 4-6 (see also [Section 6.1](#)). As PSRT safety reviews are performed weekly during the vaccination phase ([Section 9.4.1](#)), this review will also automatically include cumulative safety data from Part A participants available at this time.

This enrollment and safety review strategy allows for a single enrollment pause whilst maintaining separate randomization schemas for Part A and Part B participants. Additionally, this strategy allows for intervention of enrollment and vaccination plans for the higher dose group if safety concerns are identified in either Part A participants or the sentinel safety cohort of Part B.

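### The SAP's urticaria analysis calculates odds ratios only for covariates with unadjusted p<0.05, so those estimates are selected for being large; one tested vaccine variable also cannot be recovered from the planned output

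*SAP*

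**What the plan says.** SAP section 10.2 sets out analyses meant to generate possible explanations for the product-related urticaria. Cases are participants with any related adverse event coded to the urticaria preferred term, and everyone else is a non-case.

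- **Tests.** The SAP uses Barnard's "exact test for the following 15 binary variables at enrollment" and a Wilcoxon rank sum test for age.
- **Multiplicity.** Holm's method is applied to the p-values for "comparing each of these 16 demographic characteristics and prior histories between participants with and without urticaria", at a family-wise level of 0.05.
- **Effect estimates.** "For covariates where the unadjusted p-value was less than 0.05 for the association with urticaria, odds ratios (OR) and nominal 95% CIs were calculated". The method is mid-p median-unbiased estimation, with a correction for zero counts. No effect measure suited to age is named.
- **COVID-19 vaccine variables tested.** Besides any mRNA vaccine and any Moderna vaccine, the list has "any Pfizer COVID-19 vaccination, Moderna received as last COVID-19 vaccination, Pfizer received as last COVID-19 vaccination".
- **Table.** Counts and percentages by case status are planned with no p-value filter. The vaccine-brand rows are "receipt of any Moderna Covid-19 mRNA vaccination prior to enrollment, receipt of Moderna as last Covid-19 mRNA vaccination prior to enrollment". There is no Pfizer row.
- **Figure.** "Boxplots of days from last mRNA Covid-19 vaccination to enrollment for urticaria cases and non-cases" are planned, with point shapes that separate Pfizer from Moderna.

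**The concern.** Calculating an effect size only after a significance test has passed selects the large estimates. With few cases, a modest association can pass p<0.05 only when chance has made it look big, so the OR that is shown overstates the truth and its nominal interval is shifted with it. Holm does not help, because it acts on the p-values alone. The filter uses the unadjusted p-value, so an OR can be shown for a covariate whose Holm-adjusted p-value is well above 0.05 (the first Holm threshold is 0.05/16 = 0.0031).

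The filter and the interval also come from different methods, so near the threshold a covariate can fail Barnard's test although its mid-p interval would exclude 1.

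Separately, a variable that is tested but not tabulated would be left with a p-value and no data behind it. This section is the plan's stated route to explaining the urticaria, so an exaggerated host-factor OR could steer interpretation of that safety signal.

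**Working it through.** **1. Count of variables.** The list in section 10.2 has 15 binary variables; with age that makes 16, which agrees with the SAP. The table list covers 14 of these: 13 binary variables and age. The two missing are any Pfizer vaccination and Pfizer as last vaccination.

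**2. Inputs for the selection effect.** N = 108 is the SAP's target. The number of cases and the exposure rates are not in the documents. Assumed: 5, 7, 10, 15 or 20 cases, and 30% of non-cases exposed. With a true OR of 2, the exposure odds in cases are 2 × 0.3/0.7 = 0.857, which is 46.2% exposed.

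**3. Method.** All 2×2 tables are enumerated and weighted by their binomial probabilities.
- Filter: two-sided Barnard test (pooled score statistic, p maximised over the nuisance parameter), p < 0.05.
- OR: the value θ at which P(X > a | θ) + ½P(X = a | θ) = 0.5, where X is the number of exposed cases given the table margins and a is its observed value. The 95% limits use 0.025 and 0.975 in place of 0.5.
- If any cell is zero, 0.5 is added to all four cells and a log-normal interval is used. The interval rule for this situation is an assumption.

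**4. How the filter works, with 7 cases.** With 6/7 cases and 30/101 non-cases exposed, Barnard p = 0.026, so the OR is reported, and it is 12.5. With one exposed case fewer, 5/7 against 30/101, p = 0.058 and nothing is calculated. The mid-p OR for that table is 5.6 (95% CI 1.1 to 45), which excludes 1.

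**5. Results for a true OR of 2.**

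| Cases of 108 | Passes filter | Median reported OR | Ratio to true OR | CI coverage when reported |
|---|---|---|---|---|
| 5 | 7% | 11.1 | 5.6 | 97% |
| 7 | 7% | 10.4 | 5.2 | 72% |
| 10 | 19% | 4.8 | 2.4 | 88% |
| 15 | 12% | 5.0 | 2.5 | 82% |
| 20 | 25% | 3.6 | 1.8 | 90% |

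If every OR is reported, the median is 1.9-2.0 and coverage is 96-100%.

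**6. Stronger effects.** For a true OR of 5 the median reported ORs are 18.0, 12.5, 6.9, 6.6 and 5.4. With 10-20 cases the ratios are 6.9/5 = 1.4, 6.6/5 = 1.3 and 5.4/5 = 1.1.

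**7. What the planned table still allows.** Counts by case status fix the 2×2 table. For the example in step 4, the crude OR by hand is (5 × 71)/(2 × 30) = 5.9, close to the mid-p value of 5.6. A reader can do this for 13 of the 15 binary covariates, whatever their p-values.

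**8. The two Pfizer variables.** The SAP defines mRNA vaccination as Moderna or Pfizer. Pfizer as last mRNA vaccine is therefore the count with any mRNA vaccine minus the count with Moderna as last mRNA vaccine, by case status, provided brand is recorded. The boxplot shows the same split. Any Pfizer cannot be obtained this way, because a participant may have had both brands. One wording difference remains: the test list refers to the last COVID-19 vaccination, while the table refers to the last mRNA one. These differ only for someone whose final dose was non-mRNA after an earlier mRNA dose, and the documents do not show whether there is such a participant.

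**The case against.** The best defence is that this is a disclosed screen in an exploratory section. All 16 p-values are Holm-adjusted, the intervals are called nominal, and no primary endpoint or confirmatory claim rests on the result. All of that stands, and it sets the severity.

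Three stronger readings are tempting, and the documents do not support them.

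- A reader might infer that covariates failing the filter yield no effect information, so that no association cannot be told from too few cases. The table plan contradicts this for 13 of the 15 binary covariates: their unfiltered counts give the OR and its interval. Age has unfiltered quartiles.
- A reader might infer that any reported OR will be several times too large. That holds for a true OR of 2 with 5-7 cases, where the filter is passed only about 7% of the time. With 10-20 cases the exaggeration is 1.8-2.5 times, and for strong effects it is small. Nor is coverage uniformly poor: it is 97% in the 5-case setting.
- A reader might infer that both Pfizer variables are lost. Only any Pfizer is; the other can largely be obtained by subtraction.

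The mismatch between Barnard's test and the mid-p interval is also minor. Two exact methods will disagree near a boundary, and the example has p = 0.058 and a lower limit of only 1.1.

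**Conclusion.** The point holds in a limited form. The ORs calculated under section 10.2 are selected for being large, and neither Holm's adjustment nor the nominal label corrects them. For a true OR of 2 the median exaggeration is more than fivefold with 5-7 cases and 1.8-2.5 times with 10-20; for a true OR of 5 with 10-20 cases it is 1.1-1.4 times. These sizes rest on the assumed case counts and 30% exposure in non-cases. The direction is the same in every setting examined for a true OR of 2, including 4-15 cases with 20% or 40% of non-cases exposed.

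One tested variable, any Pfizer vaccination, has neither counts nor, unless p<0.05, an OR in the planned output. No trial conclusion depends on either matter. This is a free improvement of low severity.

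**What to change.** In SAP section 10.2:

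1. Report the mid-p OR and 95% CI for all 15 binary covariates, and a Hodges-Lehmann difference with 95% CI for age, whatever the p-value. Show them beside the unadjusted and Holm-adjusted p-values.
2. Add any Pfizer and Pfizer as last vaccination to the table by case status, and use the test list's definition of the last vaccination in the table too.

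The Barnard and Wilcoxon tests and the Holm adjustment stay as they are, so no power is lost and the error rate is unchanged. The cost is a wording change in the SAP and a few lines of programming on data already collected.
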